4.1.1. Transvaginal TCB

The patient will be placed in the lithotomic position in an US room or operating theatre. The needle will be inserted into an automatic biopsy gun. For the transvaginal approach, an 18G needle with a length of 30 cm will be used. The sample length may be 15 or 22 mm, and the required length of sample will be set. After disinfecting the vagina, the endovaginal probe with the needle held in the gun will be introduced into the vagina by the physician. The tip of the biopsy needle will be continuously visualized during the whole procedure for optimal sampling and ensure patient safety. The operator can use color/power Doppler US to increase the safety of the procedure by avoiding injuring large vessels when inserting the biopsy needle. In addition, Doppler US can help the operator identify a viable portion of the lesion without necrotic/cystic tissue, and thus minimize the risk of obtaining a sample inadequate for histological examination. When the needle is in a correct position and the penetration depth is checked, the gun will be activated by depressing the trigger button to fire the needle. After confirming successful tissue retrieval, the sample will be removed and placed into a labelled container with 10% buffered formalin. To ensure that the sample will be suitable for histological examination, we will require at least three passages of the needle into a neoplastic lesion [17, 18]. The collected tissue will be delivered to the Department of Pathology for examination and storage. At the end of the procedure, US should be continued to detect any signs of internal bleeding (e.g., “fountain sign”/turbulent flow) or other complications adjacent to the site of the biopsy. Mild internal bleeding from the biopsy site usually resolves spontaneously. If the patient suffers bleeding from the biopsy site in the vagina or in the vaginal wall, a hemostatic tamponade will be inserted inside the vagina. If an adverse event (AE) occurs, the patient will be hospitalized in the Oncogynecologic Department, depending on the severity of the AE. Data from TCB will be recorded using *TCB*

evaluation form, and details of AEs will be recorded using *the AE evaluation form*. AEs will be prospectively assessed according to the Clavien–Dindo classification (Attachment 1) [19]. AEs will be reported separately according to whether they occurred during the procedure, within 24 hours after the procedure, or within 30 days after the procedure. Furthermore, the patients will be contacted by telephone within 72 hours to enquire about their subjective assessment of the procedure.

4.1.2. Transabdominal/percutaneous TCB

The patient will lie on a bed in the US room or operating theatre. Local anesthetic will be infiltrated into the abdominal wall. For patients without a known allergy, trimecaine will be applied as a local anesthetic, and injected immediately before performing the procedure, approximately 5 minutes before TCB. The needle will be inserted into an automatic biopsy gun. For the percutaneous approach, a 16G needle with a length of 20 cm will be used. After disinfecting the skin, the operator will puncture the skin with the needle in place in the biopsy gun held in one hand, with guidance with an abdominal probe placed in the operator's other hand. The rest of procedure will be same as described in 4.1.1 Transvaginal TCB. If bleeding occurs, pressure will be applied to the site of bleeding. If pressure does not help, a stitch will be applied. AEs will be managed according to local recommendations.

4.2. DESCRIPTION OF THE EXAMINATION METHODS

4.2.1. Histopathological examination

Standard histopathological examinations will be performed for all TCB samples. To guarantee the high quality of the results, only pathologists who are highly experienced with examining TCB samples will be responsible for the histopathological examinations and other examinations.

4.2.2. Immunohistochemistry (IHC)

IHC is a pathological method to detect specific tumor antigens. IHC uses monoclonal or polyclonal antibodies to determine the distribution of tumor antigens, which may be expressed de-novo or up-regulated in a particular type of cancer [20]. IHC is often performed on tumors of unknown origin if the morphological results are inconclusive. Tumor cells may express specific intermediate filaments, such as keratin, desmin, vimentin, neurofilaments, and glial fibrillary acidic proteins [21]. By determining the expression of these and other proteins, IHC can precisely classify a tumor. Therefore, IHC is indicated by a pathologist in order to make an accurate diagnosis. Some gynecological tumors are

hormonally dependent, which means their growth is regulated by a hormone. Using IHC, we can determine the expression and distribution of hormonal receptors distribution, enabling more effective personalized treatment. IHC can also provide information about prognostic markers by identifying the enzymes, tumor-specific antigens, oncogenes, tumor suppressor genes, and tumor cell proliferation markers expressed by the tumor cells [20]. IHC can help us identify which patients are eligible for genetic screening (mismatch repair proteins – MLH1, PMS2, MSH2, MSH6 and Lynch syndrome screening) and to assess their potential eligibility for targeted therapies [22]. The gynecologist/oncologist may therefore indicate IHC to determine the patient's prognosis and choose the appropriate treatment. Thus, a great deal of information can be obtain from IHC, as for NGS, and comparing the result can be valuable.

4.2.3. Next-generation sequencing (NGS)

NGS is massively parallel sequencing that enables us to identify previously unrecognized genomic alterations in many malignancies and enable targeted therapy. NGS can be targeted using DNA or RNA panels. Using NGS, we can identify germline and somatic mutations, molecular aberrations, and specific RNA fusions, as well as their associations with malignancies. NGS can also reveal the mechanism of resistance to specific treatments. However, the main limitation of of NGS is its cost. It is also questioned how often the result of NGS will have a clinical impact and will change the patient's therapeutic strategy [22]. NGS-guided therapies include hormone therapies, pathway-specific therapies, and immunotherapies, which are associated with longer progression-free interval and longer overall survival. In gynecological tumors, the most commonly detected mutations are located in the genes *TP53*, *MYC*, *KRAS* and *BRCA1/2*. NGS examination and molecular classification can be performed at any time during the treatment course. Specific mutations can be detected in the tumor genome at initial diagnosis, or when can occur as acquired new resistance alterations after previous treatment lines. The results of NGS can optimize the therapeutic regimen and increase the opportunity for targeted therapy [23] [24]. For example, genomic profiling of endometrial cancers led to the reclassification of endometrial cancer into four groups that are distinct from the previous histological classification and are relevant to the consequent treatment of the patients [25].

NGS can also determine the tumor mutational burden (TMB), defined as the number of somatic mutations, that varies across malignancies. TMB can improve the predictive accuracy for immunotherapy outcomes, and has the potential to expand the number of candidates for treatment with immune checkpoint inhibitors [26].

We now have great expectations of liquid biopsy examination. Liquid biopsy is an essential non-invasive diagnostic test that evaluates circulating tumor cells and tumor DNA, as well as other blood markers that may be useful for guiding precision medicine. Although liquid biopsy is not a

routinely used diagnostic test, the potential applications in the diagnosis and prognosis in ovarian cancer are rapidly growing [27].

4.2.4. Immunologic examination

[figure not shown]
It is accepted that the origin and development of cancer is enabled by the evasion of immunosurveillance due to the loss of antigenicity and/or immunogenicity, and by coordinating an immunosuppressive microenvironment [28] [29]. Specific oncological treatments, including chemotherapy, radiotherapy and immunotherapy, induce an immune response beyond the expected antitumor activity. This immune response can be evaluated by immunological testing. There are some immunological indicators that are relevant to the prognosis and prediction of a treatment response, including the density, functional state, and organization of tumor infiltrating lymphocytes (TIL) [30]. Specialized methods can be used to analyze the immune contexture of tumors, and to determine biomarkers that could permit the adaptation of individual treatment approaches, as well as monitoring the response to therapy [31]. Interesting information can also be obtained by comparing the T cell profiles of samples obtained at de novo diagnosis with those obtained upon recurrence after specific therapy and is therefore useful as part of the long-term follow-up. Immunologic examination of TCB will be done consequently after the standard pathologic tests (IHC and NGS) have been performed.

STUDY DESCRIPTION

1. Referral to the Gynecologic Oncology Department
Clinical examination
Expert US
2. Inclusion and exclusion criteria assessment
Inclusion criteria
1. Presence of a pelvic/abdominal lesion with suspicion of malignancy
2. Age ≥ 18 years
3. Eastern Cooperative Oncology Group performance status grade < 3
4. Not pregnant
5. Signed informed consent form
Exclusion criteria
1. Considered by the investigator to be unsuitable for any treatment
2. Early stage disease
3. Age < 18 years
3. Informed consent signature
Included: informed consent form signed
Excluded: informed consent form not signed
4. Registration on the TRUTH electronic database
Clinical data form
5. Index tests - US
US evaluation form
6. TCB
TCB evaluation form
AE evaluation form – including telephone call to identify AEs occurring within 72 hours after the procedure
7. Histopathological report for TCB
Pathology, NGS, immunohistochemistry, and immunology evaluation form
8. Histopathological report from surgery
Final pathology evaluation form

AE: adverse event; NGS: next-generation sequencing TCB: tru-cut biopsy; US: ultrasound

Figure 1 Flow chart describing the design and patient flow in the TRUTH trial

5. STATISTICAL ANALYSIS

The power analysis was computed for adequacy/feasibility of immunological examination based on published data and a pilot study for samples obtained by TCB.

The sample size analysis was calculated for adequacy of samples obtained by TCB for histopathological diagnosis. The calculation was computed under the assumption of sample adequacy between 50-90%. The evaluated parameter was the width of 95% confidence interval for the proportion of adequate sample (Table 1-2).

With the expected adequacy of the samples in the range of 70-90%, we plan to enroll at minimum 250 subjects, in order to achieve confidence interval of $\leq 10\%$.

The analysis was computed using PASS 16 Power Analysis and Sample Size Software (2018) NCSS, LLC. Kaysville, Utah, USA, ncss.com/software/pass, by Institute of Biostatistics and Analyses (Faculty of Medicine, Masaryk University, Brno). [32, 33]

Standard descriptive statistics will be applied for the exploratory analysis, including absolute and relative frequencies for categorical variables and medians with 5th–95th percentiles and/or means with standard deviations or confidence intervals (95%) of point estimates. The statistical significance of differences in categorical variables will be assessed using the maximum likelihood chi-square test. The accuracy, adequacy, and safety will be assessed by performing receiver operator characteristic (ROC) curve analysis, after selecting appropriate predictors, and with a standard set of descriptive statistics alongside confidence intervals related to the individual predictors (area under the curve, sensitivity, specificity, positive and negative predictive value, overall accuracy).

Statistical analyses will be performed using SPSS 24.0.0.0 (IBM Corporation, 2015) statistical software.

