1. BACKGROUND AND RATIONALE

Image-guided diagnostic interventions are valuable tools in gynecologic oncology clinical practice. Several procedures are available, including core needle (tru-cut) biopsy (TCB) and fine needle aspiration biopsy (FNAB).

The purpose of performing biopsies in gynecologic practice is to obtain a representative tissue sample for a valid morphological examination. Biopsies are particularly useful for patients who are deemed unsuitable for more invasive interventions, and accelerate the process from diagnosis to therapy without the need for a period of recovery [1, 2]. In addition, in the era of personalized medicine, biopsies of gynecological cancers, either from primary, recurrent or progressive disease, have become important for characterizing the cellular pathways of the disease and to plan subsequent targeted therapy [3].

Tru-cut biopsy (TCB) is a minimally invasive method to obtain an adequate sample from the lesion and hence tailor the subsequent management avoiding unnecessary surgery. In gynecologic oncology, this technique is predominantly used in advanced ovarian cancers if primary cytoreductive surgery with no residual disease is not feasible and for patients indicated for neoadjuvant chemotherapy. Furthermore, it is useful to verify recurrent disease [4] and can be used in cases with tumors of presumed non-gynecologic origin that, in the pelvis, are mostly metastases derived from the gastrointestinal tract or breast cancer [5]. TCB can be used in combination with subjective ultrasound (US) assessment or with the assessment of different neoplasias in the adnexa (ADNEX) model to evaluate the nature of the majority of the pelvic tumor [6].

The Gynecologic Oncology Centre of the General University Hospital in Prague was among the first centers to start using TCB. Also, one of the largest retrospective studies published on this topic was done in our center. In the previous study, 190 patients were enrolled, and an adequate sample was obtained in more than 93% of all cases. In patients indicated for primary surgery or secondary debulking surgery, less than 2% of tru-cut biopsies did not coincide with the final histologic diagnoses. Regarding safety, only two bleeding complications, which were resolved by surgery, were recorded [7].

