6. STUDY TIMELINE AND SAMPLE SIZE

At Gynecologic Oncology Centre of the General University Hospital in Prague, approximately 100 women undergo TCB per year. According to the power analysis, the required study sample size is 250 cases. Therefore, the required number of the patients undergoing TCB is expected to be achieved in 2-3 years. All participants will be followed-up for 30 days after TCB to monitor any AEs. The total duration of the project is 3 years, depending on the main endpoint and power analysis.

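### The claim that 250 patients give a 95% confidence interval no wider than 10% for adequacy of 70-90% holds only from about 80% adequacy upwards

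*Protocol*

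**What the plan says.** Protocol Section 5 (Statistical Analysis) defines what was calculated: "The evaluated parameter was the width of 95% confidence interval for the proportion of adequate sample". The calculation covered adequacy from 50% to 90%, with results placed in Tables 1-2, which are not in the text at hand. The conclusion is then drawn for a narrower range: "With the expected adequacy of the samples in the range of 70-90%, we plan to enroll at minimum 250 subjects", the purpose being a confidence interval of at most 10%. The synopsis also gives 250 as the total.

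Two calculations are mentioned in the same section. One is introduced with "The power analysis was computed for adequacy/feasibility of immunological examination based on published data and a pilot study", the other with "The sample size analysis was calculated for adequacy of samples obtained by TCB for histopathological diagnosis". Section 6 (Study Timeline and Sample Size) then says: "According to the power analysis, the required study sample size is 250 cases".

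For context, Section 1 reports that in the centre's earlier retrospective series of 190 patients "an adequate sample was obtained in more than 93% of all cases". Section 6 gives the accrual basis: "approximately 100 women undergo TCB per year".

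**The concern.** The width of an interval for a proportion grows as the proportion moves from 90% towards 50%. A width promised for a whole range must therefore be checked at the end nearest 50%, here 70%. The figure of 250 looks as if it was read off at the middle of the range and then stated for all of it.

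This is the only justification given for the sample size of the primary endpoint. If it is wrong, the protocol promises a precision that the study will not have should adequacy fall in the 70s. The secondary endpoints have no separate precision statement, so a reader may carry the same promise over to them.

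**Working it through.** **Inputs.** Two-sided 95% interval, z = 1.96; n = 250; adequacy p from 70% to 90%; target total width 10% (all Section 5). The protocol names no interval method, so five common ones were tried.

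**Formulas for the total width (q = 1 − p).**
- Wald: 2z·√(pq/n)
- Wald with continuity correction (cc): the Wald width + 1/n
- Wilson: 2z·√(pq/n + z²/(4n²)) / (1 + z²/n)
- Wilson cc: U − L, with L = [2np + z² − 1 − z√(z² − 2 − 1/n + 4p(nq + 1))] / [2(n + z²)] and U = [2np + z² + 1 + z√(z² + 2 − 1/n + 4p(nq − 1))] / [2(n + z²)]
- Exact (Clopper-Pearson): difference of the beta quantiles at 0.975 and 0.025, with x = np

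**Step 1: where 250 comes from.** Solving the Wald width for n gives n = 4z²pq / 0.10².
- p = 0.80: 4 × 3.8416 × 0.16 / 0.01 = 245.9, so 246
- p = 0.70: 4 × 3.8416 × 0.21 / 0.01 = 322.7, so 323
- p = 0.90: 4 × 3.8416 × 0.09 / 0.01 = 138.3, so 139

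Smallest n for a total width of at most 10%:

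| Adequacy | Wald | Wald cc | Wilson | Wilson cc | Exact |
|---|---|---|---|---|---|
| 70% | 323 | 343 | 320 | 340 | 341 |
| 80% | 246 | 266 | 245 | 264 | 264 |
| 90% | 139 | 158 | 141 | 160 | 158 |

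The stated 250 agrees with the Wald and Wilson requirement at 80%. It agrees with no method at 70%.

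**Step 2: width delivered by n = 250.** Wald at 70%: 2 × 1.96 × √(0.21/250) = 3.92 × 0.02898 = 11.4%. Wilson at 70%: 3.92 × √(0.00084 + 0.0000154) / 1.01537 = 11.3%. Total width in %:

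| Adequacy | Wald | Wald cc | Wilson | Wilson cc | Exact |
|---|---|---|---|---|---|
| 70% | 11.4 | 11.8 | 11.3 | 11.7 | 11.7 |
| 75% | 10.7 | 11.1 | 10.7 | 11.1 | 11.1 |
| 80% | 9.9 | 10.3 | 9.9 | 10.3 | 10.3 |
| 82% | 9.5 | 9.9 | 9.5 | 9.9 | 9.9 |
| 90% | 7.4 | 7.8 | 7.5 | 7.9 | 7.8 |
| 93% | 6.3 | 6.7 | 6.4 | 6.8 | 6.7 |

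(At 75%, np = 187.5 is not a whole count; the exact figure there is the beta formula evaluated at that value.)

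**Step 3: where the target is first met.** For Wald, pq = 0.01 × 250 / (4 × 3.8416) = 0.1627, so p = 0.5 + √(0.25 − 0.1627) = 0.7955. Wilson crosses at 0.7934, Wald cc at 0.8163, Wilson cc at 0.8147 and exact at 0.8146. In whole counts this is 199/250 = 79.6% (Wald, Wilson), 204/250 = 81.6% (Wilson cc, exact) and 205/250 = 82.0% (Wald cc).

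**Step 4: alternative reading.** If 10% meant the half-width, 250 would meet it throughout (Wald: 11.36/2 = ±5.7% at 70%). But then 78 to 91 patients would be enough at 70%, so this reading does not account for 250.

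**The case against.** The target sentence does not itself contain the word width. Read as ±10 percentage points it is true over the whole of 70-90%, and a sample larger than precision requires could have other grounds, such as the multivariable analysis in Section 2.4. This reading is possible but weak: the same section names the width as the quantity evaluated, and a total width of 10% at 80% adequacy gives 245 or 246, close to the stated number.

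Tables 1-2 are not visible here. They may already list the correct widths and identify the interval method, in which case the fault is confined to one summary sentence. They cannot make that sentence true at 70%, because the width there exceeds 10% under every method tried.

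The strongest part of the objection concerns weight, and it stands. The study estimates a proportion in a single arm, and no test or go/no-go rule hangs on the 10% figure. The primary endpoint may well land above 90%, given the centre's earlier series. It is also fair that calling a sample size calculation a power analysis is common loose usage. That wording is a request for clarification and adds nothing to the arithmetic.

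**Conclusion.** The concern holds. On the natural reading, total width of a two-sided 95% interval, 250 patients do not give at most 10% across 70-90% adequacy. They do so from about 80% (Wald, Wilson) or about 82% (exact, continuity-corrected). At 70% the excess is 1.3 to 1.8 percentage points of total width.

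The error is certain on that reading but its consequence is small. It would be felt only if adequacy, for histopathology or for a secondary examination judged by the same standard, came out below roughly 80%. At 93% the width is 6.3% to 6.8%. The calculation assumes that all 250 patients count in the denominator. Section 2.4 restricts that denominator to patients who underwent the biopsy, so any enrolled patient without one would widen the interval slightly further.

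The statement should be corrected because it is the stated basis of the sample size. It gives no reason to question the conduct of the study.

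**What to change.** Keep 250 and replace the precision sentence in Section 5 with, for example:

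> With 250 patients who undergo TCB, the total width of the 95% confidence interval (Wilson) is 7.5% at 90% adequacy, 9.9% at 80%, 10.7% at 75% and 11.3% at 70%. It is at most 10% for adequacy of about 80% or higher.

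The method named should be the one behind Tables 1-2. If that was the exact interval, the figures are 7.8%, 10.3%, 11.1% and 11.7%, and the claim should be limited to about 82% or higher.

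In the same paragraph, say whether 250 was derived for histopathology, the primary endpoint, or for the immunological examination, and use the same term for that calculation in Section 6.

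The cost is one reworded paragraph and one term, with no extra patients and no change to the analysis. The stated precision becomes slightly less favourable at the low end. Enlarging the study instead would be out of proportion: at about 100 biopsies a year, 320 to 343 patients would take 320/100 = 3.2 to 343/100 = 3.4 years, longer than the 3 years given in Section 6, although that section lets the duration depend on the calculation.

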2.3. Additional endpoints

1. To evaluate which factors affect the primary and secondary endpoint, including:
 - a. tumor origin
 - b. size of the tumor
 - c. presence of ascites
 - d. body mass index (BMI)
 - e. biopsy site
 - f. biopsy approach transvaginal, transrectal vs. transabdominal
 - g. disease status – the first diagnosis, the first and other recurrence or progression
 - h. previous treatment modality – chemotherapy, anti-angiogenic therapy, PARP inhibitor therapy, hormonal therapy, or radiotherapy
2. To evaluate the overall safety of TCB
3. To evaluate the overall accuracy of TCB for complex classification of pelvic and abdominal tumors

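### Section 5 plans ROC performance figures after predictor selection in the same single-centre cohort with no correction for selection; if selection uses the outcome data, AUC, sensitivity and specificity are biased upward

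*Protocol*

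**What the plan says.** Protocol section 5 states that accuracy, adequacy and safety will be assessed by "receiver operator characteristic (ROC) curve analysis, after selecting appropriate predictors". The results are to be given "alongside confidence intervals related to the individual predictors (area under the curve, sensitivity, specificity, positive and negative predictive value, overall accuracy"). No selection rule, cut-off rule, data split, resampling or optimism correction is stated, and the protocol describes one centre and one cohort.

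The candidates come from section 2.3: "To evaluate which factors affect the primary and secondary endpoint, including" eight headings, a to h. Heading h contains five prior treatments, so there are 7 + 5 = 12 candidate variables. Section 2.4 adds a multivariable analysis of selected variables for accuracy and adequacy. One of its examples, the number of biopsies, is not on the section 2.3 list, so the candidate set is open.

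The sample size was set for something else: "The evaluated parameter was the width of 95% confidence interval for the proportion of adequate sample". Section 2.4 restricts accuracy to patients with an adequate sample who went on to surgery, so that analysis uses fewer than 250 patients.

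**The concern.** When predictors are picked because they separate the outcomes in a data set, and their discrimination is then measured in that same data set, the measure includes the chance separation that got them picked. The apparent AUC is then too high, as are sensitivity and specificity at a cut-off tuned to the same data. Confidence intervals that ignore the selection are centred on the inflated value.

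The bias grows as the rarer outcome class shrinks and as candidates are added. Here the rarer class is the inadequate samples, the complications or the discordant diagnoses, and the centre's own history suggests that all three are few. Section 7 presents evaluation by location, size and other factors as a contribution of the study, so readers will take these figures as evidence on what determines an adequate biopsy. Noise could be reported as a moderate predictor.

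**Working it through.** **The plan's own figure.** Section 5 gives no number for the ROC analysis. Its only figure is N = 250, for a 95% interval of at most 10%. Wald full width is 2 × 1.96 × √(p(1−p)/250): 11.4% at p = 0.70, 9.9% at 0.80, 7.4% at 0.90. The N needed for a width of 10% is 323, 246 and 139 respectively. So 250 fits 80% adequacy and above. It is a precision target for one proportion and carries no allowance for choosing among predictors.

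**Size of the rarer class.**
- Planning: "With the expected adequacy of the samples in the range of 70-90"%, so 0.30 × 250 = 75 down to 0.10 × 250 = 25 inadequate samples.
- Earlier series: "an adequate sample was obtained in more than 93% of all cases", so at most 0.07 × 250 = 17.5.
- Safety: 2 bleeding complications in 190 patients (section 1), so 250 × 2/190 = 2.6.
- Accuracy: discordance below 2% (section 1), so fewer than 0.02 × 250 = 5 even if every patient were operated on. The number operated on is not given.

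**Chance of a false predictor.** With 12 independent null candidates each tested at 0.05 (level assumed; none is stated), P(at least one significant) = 1 − 0.95^12 = 0.46. Simulation at n = 250 gives 0.46-0.56 over 7-30% inadequate.

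**Hand check for the best single predictor.** Under the null, the standard error of the AUC is √((n+1)/(12·n1·n0)). The expected largest of 12 absolute standard normal values is 1.96, so the expected best apparent AUC for continuous predictors is about 0.5 + 1.96 × SE.
- 75 v 175: SE 0.040, AUC 0.58
- 25 v 225: SE 0.061, AUC 0.62
- 17.5 v 232.5: SE 0.072, AUC 0.64

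Binary predictors give slightly less because of ties.

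**Simulation, no true predictor, n = 250, 12 candidates.** Mean apparent AUC; a range is the spread between two simulations with separately chosen assumptions.

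| Inadequate | Best single | Best three | p<0.05 screen* | All candidates |
|---|---|---|---|---|
| 30% | 0.57 | 0.61 | 0.59 | 0.64-0.65 |
| 20% | 0.58 | – | 0.61 | 0.68 |
| 10% | 0.60-0.61 | 0.67 | 0.64 | 0.70-0.74 |
| 7% | 0.62-0.64 | 0.69 | 0.67 | 0.74-0.78 |

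*Only runs in which something passed; in roughly half nothing did.

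The true AUC is 0.50 in every row. The all-candidate model scored on 1,000 fresh patients averages 0.50, and 5-fold cross-validation with selection repeated inside each fold also averages about 0.50. In the simulation with the higher all-candidate values (16 model terms), the null model reaches an apparent AUC of 0.70 or more in 5%, 25%, 78% and 92% of runs from the top row to the bottom. At 7% inadequate its mean apparent sensitivity and specificity at the best cut-off are 0.79 and 0.72.

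**Rare outcomes** (runs with fewer than two events dropped). At 1% events in 250 patients, the null apparent AUC is 0.80 for the best single predictor, 0.84 after a p<0.05 screen (runs with a selection) and 0.97 with all candidates. For accuracy, with an assumed 100 operated patients and 2% discordant, the figures are 0.81, 0.87 and 0.98.

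**The case against.** The strongest reply is that the text does not say that selection uses the outcome. Appropriate predictors could mean clinically appropriate ones, and most candidates are listed in advance. That stands, and the finding is therefore conditional. Data-driven selection remains the natural reading, because the same paragraph plans significance tests on the study data and no shortlist is given.

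A second reply is that selection rules and validation often sit in a statistical analysis plan, which is not at hand. Silence alone would not be a finding. But section 5 does not defer the matter: it fixes the order, selection and then ROC, and names the outputs. Followed literally under the natural reading, that gives biased figures.

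Third, the performance measures are tied to individual predictors, and section 2.4 does not say that an AUC will come from the multivariable model. On that reading the best-single column applies, and its bias is modest over the planning range.

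Two stronger readings are tempting. A reader might infer that the results will look useful even if nothing predicts. At 70-80% adequacy the screened null AUC is only about 0.60 and the best single predictor about 0.58, which would impress few readers. A reader might also infer that patients would be selected for or against biopsy on such results. The protocol proposes no cut-off for practice and no prediction tool.

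**Conclusion.** The point holds in conditional form. If predictors or cut-offs are chosen with the outcome data, the planned performance measures are biased upward at every adequacy level examined. The excess in AUC for the best single predictor is about 0.07-0.11 over the planned 70-90% range and 0.12-0.14 at 93%. For the best three it is 0.11-0.17 and 0.19. With all candidates at 93% it is 0.24-0.28. It is far larger for safety, and for accuracy, which also uses only the operated subset with an adequate sample.

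The figures rest on assumed predictor prevalences and coding, independent predictors, a 0.05 screen or a best-three rule, and (for accuracy) 100 operated patients. The safety rate counts only the two bleeding events of the earlier series; a broader definition would give more events and less bias. Direction and rough size are reliable; second decimals are not. These analyses serve additional endpoints, and the primary adequacy proportion is not affected.

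**What to change.** Amend section 5 in one of two ways.

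1. Name two or three predictors in advance on clinical grounds and drop data-driven selection. Any cut-off should also be fixed in advance.
2. Keep selection, and add for example: *Predictor selection and the choice of any cut-off are repeated within each resample (repeated stratified cross-validation). Conclusions rest on the corrected AUC, sensitivity, specificity and predictive values; uncorrected values are labelled as apparent.*

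Neither needs extra patients or procedures; the cost is a sentence and a few lines of code. Reported performance will be lower. With 17 to 25 inadequate samples, five folds leave about 3 to 5 of them per fold, so cross-validated sensitivity and cut-offs will be imprecise. That favours the first option if adequacy turns out at 90% or above.
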